| Study Visit Number a | n/a                    | 1              | 2                        | 3                  | 4                  | 5                  | 6              |
| Study App Deactivation          |                        |                |                          |                    |                    | X g     |                |
| Concomitant Medications         | X                      | X              | X                        | X                  | X                  | X                  | X              |
| Adverse Events                  | X                      | X              | X                        | X                  | X                  | X                  | X              |

[figure not shown]
Abbreviations: DOSE-Nonadherence measure = Domains of Subjective Extent Nonadherence measure; ET = Early Termination; ID-CM = Identify Chronic Migraine; MIDAS = Migraine Disability Assessment Scale; MSQ = Migraine-Specific Quality-of-Life Questionnaire; PGI-C = Patient Global Impression of Change scale;

- a. All study visits are virtual and conducted via telemedicine.
- b. Screening Visit may occur up to fourteen (14) days before the run-in period.
- c. Follow-Up activities, to include revealing the trial hypothesis, to occur within one week of the final intervention period visit. This is at least one day after the Week 12 visit (between Day 86 and Day 92) or at least one day, but no more than seven days, after an Early Termination visit.
- d. Only the eDiary component of the Study App is used by the participant to complete run-in period activities. The run-in period consists of 28 days of data. However, per Study App design, participants may enter Day 28 data until Day 30. The Baseline Visit window will begin after Day 30.
- e. The full Study App is used every day by the participant during the indicated period.
- f. Adherence checks occur at baseline to confirm eligibility and as needed throughout the intervention period when a participant does not perform Study App Activities for 3 calendar days per Section 6.4.
- g. After completion of the intervention period (Day 84), the Study App will become inert. After Day 84, or upon study withdrawal, participants will not have continued access to the content provided by the Study App.

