#### 4.1.1. Screening Period (Day -42 to Day -29)

All participants will enter a screening period of up to 14 days to determine eligibility. Eligible participants must report having had at least four migraine days per month in the three months prior to the Screening Visit (a month is defined as 28 days).

Prior to entering the screening period, participants will be asked to download the App (separate from the Study App) in order to provide consent to the trial and complete trial assessments, including self-administered scales.

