## 7. DISCONTINUATION OF STUDY INTERVENTION AND PARTICIPANT DISCONTINUATION/WITHDRAWAL

#### 7.1. Discontinuation of Study Intervention

In rare instances, it may be necessary for a participant to permanently discontinue study intervention. If study intervention is permanently discontinued, the participant will complete early termination assessments as per the SoA (Section 1.2).

Events that could result in permanent discontinuation of study intervention include:

- Nonadherence
- Use of prohibited concomitant medications
- Use of prohibited recreational medications
- Investigator's discretion

The Study App on the discontinued participant's smartphone device will be disabled as described in Section 6.2.

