### 7.2. Participant Discontinuation/Withdrawal from the Study

Study staff should make every effort to encourage participants to remain in the study and to continue to use the Study App. A participant may withdraw from the study at any time at their own request or may be withdrawn at any time at the discretion of the investigator for safety, behavioral, or compliance reasons. This is expected to be uncommon.

A participant cannot withdraw consent for use of data already collected as part of the study. If the participant withdraws consent for disclosure of future information, the sponsor may retain and continue to use any data collected before such a withdrawal of consent.

Participants who prematurely discontinue study participation must complete the early termination procedures as described in the SoA (Section 1.2). Participants who discontinue use of the Study App prematurely should ideally be observed until the end of the study as if they were still using the Study App. The Study App on the discontinued participant's smartphone device will be disabled as described in Section 6.2. For all participants, the reason for discontinuation (e.g., AEs) must be recorded in the eCRF. These data will be included in the study database and reported.

Participants who are not actively using the Study App may be less motivated to adhere to the study visit schedule. Investigators and study staff should work to detect early signs of waning interest and encourage continued participation.

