6. STATISTICAL CONSIDERATIONS

6.1. General

For continuous variables, summary tables will provide the number of observations [n], mean, standard deviation, median, minimum, and maximum. For categorical variables, summary tables will provide the number of observations [n] and frequency of each category (including missing data). Tabulations will be presented by treatment and overall, when appropriate. Modelling and testing will be described for each endpoint.

Study day for specific measurement is calculated as (date – date of baseline visit). Run-in period will include study days -28 until -1. Day 0 is the baseline day and days >=1 are treatment period days.

Measurements taken at Early Termination visit/withdrawal will be presented in listings but will not be included in summaries and analyses.

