8.5.5. Change in the number of headaches with at least moderate severity from baseline (28-day run-in period) to Week 12 (previous 28 days, Week 9 through Week 12)

This endpoint will be performed on the mITT analysis set, in addition to the ITT analysis set.

Each recorded headache's severity will be scored in the following manner:

- None = 0
- Mild = 1
- Moderate = 2
- Severe = 3

Headaches that started at one period and ended in the following period will be assigned to the period in which the headache started.

The change from run-in will be calculated as (Weeks 9-12 number of headaches with at least moderate severity – run-in number of headaches with at least moderate severity).

An ANCOVA model will be used to analyze this endpoint. The dependent variable is the change in number of headaches with at least moderate severity from run-in period to Week 9-12 for each participant.

The model will adjust for the following covariates: treatment arm and number of headaches with at least moderate severity at run-in period

This analysis will use observed data only.

8.5.6. Change from baseline in the Migraine-Specific Quality-of-Life Questionnaire v2.1 (MSQ) total score at Week 12

The MSQ is a 14-item questionnaire that is completed at baseline, Week 4, Week 8, and Week 12. Each item consists of 6 possible responses, scored 1 to 6. Higher scores represent more severe migraines.

For the purpose of calculating the MSQ total score, the responses to the 14 items will be reverescoded (scores 1,2,3,4,5,6 will be converted to 6,5,4,3,2,1 respectively)

For each visit, the MSQ score (after reverse-coding) will be calculated as:

Total score = ([sum of the 14 reversed item scores - 14] / 70) * 100

In case of missing items, the MSQ score for the visit will be considered missing.

An ANCOVA model will be used to analyze this endpoint. The dependent variable is the change from baseline in MSQ to week 12 for each participant.

The model will adjust for the following covariates: treatment arm and baseline MSQ.

This analysis will use observed data only.

8.5.7. Change from baseline in the Migraine-Specific Quality-of-Life Questionnaire v2.1 (MSQ) total score at Week 8

This endpoint will be analyzed in the same manner as described in Section 8.5.6, using the Week 8 assessment.

8.5.8. Change from baseline in the Migraine-Specific Quality-of-Life Questionnaire v2.1 (MSQ) total score at Week 4

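### Permanently stopping the Study App reads as an exit in Protocol 7.1, the Schedule and (for prohibited medication) SAP 2.2, but not in Protocol 7.2, so later MSQ, MIDAS and PGI-C scores may be lost or collected after the hypothesis is disclosed

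*Protocol*

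**What the plan says.** **Stopping the intervention.** Protocol Section 7.1 concerns the intervention, not the study: "If study intervention is permanently discontinued, the participant will complete early termination assessments as per the SoA (Section 1.2". It describes such cases as rare. The reasons it lists include nonadherence and use of prohibited medication.

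**Leaving the study.** Section 7.2 prescribes the same step for a different group: "Participants who prematurely discontinue study participation must complete the early termination procedures as described in the SoA (Section 1.2". It then says that people who stop the app early "should ideally be observed until the end of the study as if they were still using the Study App".

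**Schedule (Section 1.2).** There is one combined Week 12/ET column, in which MSQ, MIDAS and PGI-C are all marked. Footnote c places follow-up, including disclosure of the trial hypothesis, "at least one day, but no more than seven days, after an Early Termination visit". No column or note covers visits after that.

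**SAP Section 2.2.** A participant who uses prohibited medication is discontinued from the study and the app is disabled. The strategy is labelled treatment policy.

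**Where the scales are completed.** Section 4.1.1 describes an app "separate from the Study App) in order to provide consent to the trial and complete trial assessments", and includes the self-administered scales among those assessments.

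**Analysis.** SAP Section 6.1: "Measurements taken at Early Termination visit/withdrawal will be presented in listings but will not be included in summaries and analyses". For both MSQ (SAP 8.5.6) and MIDAS (SAP 8.5.9): "This analysis will use observed data only". SAP 8.5 nevertheless assigns the secondary analyses to the ITT set.

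**The concern.** One event, permanently stopping the app, has two instructions attached to it. One looks like an exit: ET, follow-up, disclosure, nothing further. The other asks for continued observation but supplies no visits. Staff handling the same situation could reasonably act differently.

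Either route damages the scale endpoints. On the exit route the participant gives one set of scores at ET, which the SAP does not analyse, and nothing at Week 12. The MSQ and MIDAS comparisons are then restricted to people who kept using their assigned app. That selection occurs after randomisation and may depend on how well each app worked or was liked. If a participant goes through ET follow-up and is then observed further, the later self-reports come from someone who has already been told that one product was expected to do better. The hypothesis blind in Sections 4.1 and 6.3 is meant to prevent that.

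The loss looks avoidable, because disabling the Study App does not by itself disable the app in which the scales are completed.

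**Working it through.** **1. The texts applied to one case.** Suppose the app is permanently stopped on Day 33 (Week 5).
- Section 7.1: ET assessments at that time.
- Footnote c: follow-up and disclosure 1 to 7 days later, so Day 34 to Day 40.
- Schedule: the Week 8 visit is Day 57 and the Week 12 visit is Day 85. These fall 57 − 40 = 17 and 85 − 40 = 45 days after the latest follow-up date.
- Section 7.2: the participant should ideally still be observed on those days.
- Section 4.1.5: disclosure belongs at the conclusion of participation. If Section 7.2 is followed, that has not been reached by Day 40.

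An assessment at stopping is compatible with continued visits. The conflict comes from the shared column and footnote c, which attach final follow-up and disclosure to any ET visit.

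**2. Can the ET scores stand in?** Not as planned: SAP 6.1 confines them to listings. For MIDAS they would also be a poor substitute, since Section 8.1.5 gives a 3-month reference period and a Week 5 score reaches back before randomisation.

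**3. The plan's own figures.** Inputs from Protocol 9.2: difference 1.6, SD 5.8, two-sided alpha 5%, power 85%, drop-out 15%.
- Normal approximation: n per arm = 2 × (1.960 + 1.036)² × (5.8/1.6)² = 236. The exact two-sample t-test gives 236.93, so 237 per arm and 474 in total.
- 474 / 0.85 = 557.6, so 558. Both stated figures reproduce.

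**4. How many people.** 558 × 0.15 = 83.7, about 84. This is a ceiling: the 15% is not broken down and would include withdrawals and losses to follow-up that no visit schedule recovers.

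**5. Precision.** Let f be the share of the 84 who could still give Week 12 scores (not in the documents, so shown as a range). Observed N = 474 + 84f, and the standard error relative to N = 474 is √(474/N).

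| f | N | Relative SE |
|---|---|---|
| 0 | 474 | 1.00 |
| 0.25 | 495 | 0.98 |
| 0.50 | 516 | 0.96 |
| 0.75 | 537 | 0.94 |
| 1 | 558 | 0.92 |

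**6. Which effect is estimated.** Assume equal stopping, with fraction q in both arms; those who continue have mean effect d and those who stop have r × d. The all-randomised effect is d × [(1 − q) + qr], while the observed-only effect is d. Overstatement = 1 / [(1 − q) + qr] − 1.

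| q | r = 0 | r = 0.5 |
|---|---|---|
| 5% (assumed) | 1/0.950 − 1 = 5.3% | 1/0.975 − 1 = 2.6% |
| 15% (ceiling) | 1/0.850 − 1 = 17.6% | 1/0.925 − 1 = 8.1% |

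This suits a mean difference, such as the MSQ ANCOVA. It does not apply to MIDAS, which is compared by a Wilcoxon rank-sum test. Neither document gives an effect size or SD for MSQ, MIDAS or PGI-C, so their power cannot be computed.

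**The case against.** The strongest reply is that Section 7.1 never says the participant leaves the study, and that 7.2 expects otherwise. The end of 7.2 notes that people no longer using the app may be less inclined to keep to the visit schedule and tells staff to encourage them, which presupposes that they remain on it. A reader might infer that everyone who stops the app is removed and that their later scores are never collected. The documents do not support that: 7.2 asks for continued observation, and each scale is taken once at ET.

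Other parts of the reply also stand:
- Stopping is described as rare, and SAP 2.2 lists lack of adherence separately from early discontinuation, so drifting off the app need not trigger ET.
- Reading the 84 as an expected loss would be wrong, for the reason given in step 4 of the working.
- The sample of 558 was set to leave 474 evaluable, so a wider standard error at 474 is no shortfall against plan.
- MSQ and MIDAS are secondary, with nominal p-values not used for inference (SAP 8.6), and PGI-C is exploratory.
- SAP 6.1 excludes only ET and withdrawal values. A score from an off-app participant at a scheduled visit would already count as observed.
- Section 6.2 and part of SAP 6.3 are not in the public text. The separate-app statement sits in the screening section, so its use after stopping is a reasonable inference rather than a stated rule.

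None of this removes the conflict. Section 7.2 is worded as an ideal and has no schedule behind it, whereas 7.1 is an instruction and footnote c sets a time limit. The SAP, which prevails over the protocol under its Section 1, treats prohibited-medication use as leaving the study, while 7.1 lists it only as a possible reason for stopping the intervention.

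**Conclusion.** The point holds as a conflict between texts with a limited, avoidable cost. It should be corrected, but it does not threaten the trial's main conclusion. Depending on which text staff follow, later MSQ and MIDAS scores and the Week 12 PGI-C may be missing, or may be given after the hypothesis is disclosed. The documents do not say that treatment allocation is revealed at that visit, so the breach concerns the hypothesis blind only.

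The size depends on how many people stop the app yet could still be followed, which the documents do not state. The percentages in step 6 rest on an assumed 0 to 50% retained effect and equal stopping in the two arms; unequal stopping would add a bias that cannot be sized from the documents.

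A reader might extend this to the primary endpoint. That is not supported here: monthly migraine days come from the eDiary inside the Study App, missing diary days are imputed, and keeping the scale visits would neither restore nor change those data.

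**What to change.** Reconcile Protocol 7.1, 7.2, the Schedule with footnote c, and SAP 2.2, so that stopping the app and leaving the study are separate events with separate procedures.

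- State that a participant who permanently stops the Study App but does not withdraw from the study keeps the remaining scheduled scale assessments: MSQ and MIDAS at whichever of Weeks 4, 8 and 12 are still to come, and PGI-C at Week 12. Confirm that these are completed in the separate assessment app.
- Reserve the ET use of the Week 12/ET column, the 1 to 7 day follow-up and the hypothesis disclosure for people leaving the study.
- Make the protocol and SAP agree on whether prohibited-medication use ends study participation or only the intervention. Which it should be is for the sponsor to decide.
- Confirm in the SAP that scores from off-app participants at scheduled visits are analysed as scheduled-visit data.

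This is a data-collection rule and leaves unchanged when the intervention is stopped. The cost is wording, plus at most three remote visits with questionnaires for each such participant, with no new instruments or extra participants. The scale estimates may come out somewhat less favourable, because they would describe more of those randomised.

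### SAP 2.2 labels its handling of prohibited medication treatment policy but stops data collection at that event, so later Weeks 9-12 migraine days are imputed; keeping the eDiary open is an optional alignment

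*Protocol*

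**What the plan says.** **Estimand.** SAP 2.2 targets the effect on MMDs whatever the use of prohibited medication, adherence or early termination, and assigns all three events to the treatment-policy strategy. For prohibited medication it discontinues the participant from the study, disables the Study App, and analyses the data accumulated up to that moment. For early discontinuation it treats data that do not exist afterwards as missing and imputes them. The imputation is multiple imputation under missing at random (MAR) (Protocol 9.4.4), with 100 completed datasets (SAP 8.1.3).

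**Where MMDs come from.** Protocol 8.1.2 has participants record migraine days in the Study App. Protocol 4.1.2 and 4.1.3 describe the eDiary as a component of that app. No other source is visible. Measurements at the Early Termination visit are listed but not analysed (SAP 6.1).

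**Stopping the intervention.** Protocol 7.1 begins: "In rare instances, it may be necessary for a participant to permanently discontinue study intervention". Its list is introduced by "Events that could result in permanent discontinuation of study intervention include" and includes nonadherence and prohibited medication. These participants go to early termination assessments, and "The Study App on the discontinued participant's smartphone device will be disabled as described in Section 6.2". Protocol 7.2 repeats the disablement, yet also says that people who stop using the app should ideally be followed to the end of the study.

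**Close-out.** Note c of the schedule (Protocol 1.2) states: "Follow-Up activities, to include revealing the trial hypothesis, to occur within one week of the final intervention period visit". After early termination the window is "or at least one day, but no more than seven days, after an Early Termination visit".

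**The concern.** A treatment-policy strategy uses the outcome that occurs after the intercurrent event. In the prohibited-medication rule of SAP 2.2, the event itself ends collection of the outcome. The label and the data flow therefore disagree, and this can be seen without Section 6.2.

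For others who stop the intervention, the same would follow if disabling the app includes the diary. Protocol 7.2 asks for observation to the end of the study, but no visible text says how MMDs would then be recorded.

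What is at stake is which data inform Weeks 9-12 for these people. MAR imputation borrows from participants in the same arm who stayed on the app. In the CT-132 arm it can credit benefit that was lost when the app was switched off. Early disclosure of the hypothesis adds a practical obstacle: a diary kept after the reveal is no longer blind to it.

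**Working it through.** **1. The plan's own figures.** Protocol 9.2 gives a difference of 1.6 MMD, SD 5.8, 85% power and two-sided alpha 5%. A two-sample t-test needs 236.93, so 237 per arm and 474 in total. Allowing for 15% dropout, 474 / 0.85 = 557.6, so 558, or 279 per arm. Both stated numbers reproduce. The standard error with everyone contributing is 5.8 × √(2/279) = 0.491.

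**2. Overstatement when the CT-132 effect is lost after stopping.**

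Overstatement = x × 1.6 × (1 − k) × (1 − b)

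- x: share who stop the intervention. Assumed 2% or 5%, which is 0.02 × 558 ≈ 11 or 0.05 × 558 ≈ 28 people. The documents say rare and give no number.
- k: share of the effect retained after stopping. Assumed 0 or 0.5.
- b: slope of the imputation on the participant's own earlier diary. Assumed 0 (ignored) or 0.6. Conditioning helps only where that earlier diary already shows the smaller benefit. If the benefit disappears only after stopping, the b = 0 rows apply.

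| x | k | b | Overstatement (MMD) | In SE |
|---|---|---|---|---|
| 2% | 0 | 0 | 0.032 | 0.07 |
| 2% | 0.5 | 0 | 0.016 | 0.03 |
| 2% | 0 | 0.6 | 0.013 | 0.03 |
| 2% | 0.5 | 0.6 | 0.006 | 0.01 |
| 5% | 0 | 0 | 0.080 | 0.16 |
| 5% | 0.5 | 0 | 0.040 | 0.08 |
| 5% | 0 | 0.6 | 0.032 | 0.07 |
| 5% | 0.5 | 0.6 | 0.016 | 0.03 |

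The formula counts every stopper as having no Weeks 9-12 diary. Someone who stops during those weeks keeps the days already entered, so their contribution is smaller.

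A simulation (20 runs of 400,000 per arm, k = 0) agrees. At x = 5% it gives 0.080 without conditioning, and 0.032 with a correlation of 0.6 and an earlier diary that already shows the loss. At x = 2% it gives 0.031 and 0.013.

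**3. What an open diary recovers.** If a share r of these participants would still report, the amount removed is r × overstatement.

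- r = 50% (about 6 to 14 people): 0.003 to 0.040 MMD.
- r = 25% (about 3 to 7 people): 0.002 to 0.020 MMD.

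**4. Upper bound.** If the whole 15% dropout allowance (about 84 of 558) were of this kind, with k = 0 and b = 0, the overstatement would be 0.15 × 1.6 = 0.24 MMD, or 0.24 / 0.491 = 0.49 SE. The documents do not suggest this: the 15% has no breakdown by reason, and Protocol 7.1 calls these stops rare.

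**5. Prohibited medication.** The medication may itself reduce migraine days, and imputation leaves that out. If it lowers MMDs by m in users, with use p_C in the control arm and p_T in the CT-132 arm, the extra error in the estimated benefit is (p_C − p_T) × m. It favours CT-132 if controls use more, works against it if they use less, and vanishes if use is equal. The documents give neither p nor m, so this part cannot be sized.

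**The case against.** **Withheld text decides the wider case.** Section 6.2 defines what disabling means and is not public. It may leave the diary running. Note g of the schedule fits that reading: "After Day 84, or upon study withdrawal, participants will not have continued access to the content provided by the Study App". So does Protocol 4.1.3, which has the eDiary used throughout the study. This stands. For Protocol 7.1 the point is conditional. It is not conditional for prohibited medication, where SAP 2.2 itself removes the participant and sets the data cut-off.

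**The SAP already imputes only what is absent.** For early discontinuation this is right, and diary days that exist are not excluded. Only the prohibited-medication rule carries a cut-off.

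**A reader might infer that nonadherent participants are routinely cut off.** The documents do not support this. Protocol 7.1 says nonadherence could lead to discontinuation. Note f calls for an adherence check "as needed throughout the intervention period when a participant does not perform Study App Activities for 3 calendar days", which is a check and not removal. People who stop doing tasks may also stop the diary, and an open diary would recover little from them.

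**A reader might infer that the primary result is at risk.** That is not supported either. The shift is a small fraction of one standard error at plausible rates, the sample size allows for dropout, and the tipping-point analysis (SAP 8.3.1) probes departures from MAR. That analysis tests the assumption but does not supply the missing outcomes.

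**The cost is not documented.** This is fair. An eDiary-only mode is shown only for the run-in, before the full app is unlocked.

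**Conclusion.** The point holds in a limited form. For prohibited medication, SAP 2.2 claims treatment policy while ending data collection at the event, so the remaining Weeks 9-12 MMDs are imputed. For others who stop the intervention, the same follows only if Section 6.2 closes the diary, and that cannot be seen.

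The likely size is about 0.01 to 0.08 MMD (0.01 to 0.16 SE). This rests on an assumed 2-5% stopping, no or half the effect retained, and imputation that credits the arm's on-app effect; the visible part of SAP 6.3 does not give the imputation rules. The direction for prohibited medication is unknown. The change is optional and would bring data collection into line with the plan's own estimand and with the follow-up wish in Protocol 7.2.

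**What to change.** (a) In SAP 2.2, have prohibited medication discontinue the participant from the intervention and not from the study. This also matches Protocol 7.1, which lists such use as a possible reason to stop the intervention. State that diary days reported afterwards enter the primary analysis and that only unreported days are imputed.

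(b) In Protocol 7.1 and 7.2, lock only the therapeutic content and keep the eDiary open through Day 84 for participants who stop the intervention but have not withdrawn from the study or withdrawn consent. If Section 6.2 already does this, a cross-reference is enough.

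(c) For these participants, keep the early termination and safety contact as scheduled and delay only the reveal of the hypothesis until after Day 84.

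Investigator-initiated withdrawal under Protocol 7.2 need not change.

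Cost: wording in the protocol, schedule and SAP, and an app configuration. Returning an unlocked app to eDiary-only mode has to be confirmed with the app team. No extra participants are needed. The estimate may become slightly less favourable, and the gain is limited to days actually reported. If follow-up is already complete, only the SAP wording can still be changed.
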